Clinical Protocol 07 January, 2018 – Version 3.1

An Open-Label Pilot Study to Assess the Safety and Potential of Oral Insulin to Reduce Liver Fat Content in Patients with Nonalcoholic Steatohepatitis (NASH)

ORA-D-N01

INVESTIGATOR STUDY CENTER

[name] (PI)

Liver Unit, Dept. of Gastroenterology and Liver Diseases, Division of Medicine
Hadassah University Medical Center
[name]

Confidential

INTRODUCTION

Nonalcoholic fatty liver disease (NAFLD) and nonalcoholic steatohepatitis (NASH) are global public health issues closely associated with the worldwide epidemics of diabetes and obesity.¹⁻³ NAFLD encompasses the spectrum of liver disease in patients with no significant alcohol consumption ranging from fatty liver to steatohepatitis and cirrhosis.¹ Nonalcoholic fatty liver (NAFL) is characterized by the presence of liver infiltration of fat (hepatic steatosis) with no evidence of hepatocellular injury in the form of ballooning of hepatocytes or no evidence of cirrhosis.¹ The risk for progression to cirrhosis and liver failure in these patients is minimal. NASH is defined by the presence of hepatic steatosis and inflammation with hepatocyte injury (ballooning) with or without cirrhosis.¹ NASH can progress to cirrhosis, liver failure and occasionally liver cancer.

NAFLD is now considered to be the commonest cause of chronic liver disease in developed countries with as high as 30% of the general population affected.^{2,4} In newly identified cases of chronic liver disease in a US survey, 39% had NAFLD.² A high prevalence of NASH among NAFLD cases has been reported²: up to 55% in patients with elevated aminotransferases^{5,6}, as high as 49% in morbidly obese patients^{7,8}, and 67% in a subset of patients with incident chronic liver disease.⁹

Half a billion adults worldwide are estimated to be obese and 1.5 billion are overweight or obese.^{10,11} Overall, about two-thirds of the population in the developed world have a BMI greater than 25 kg/m².¹² Primary NAFLD/NASH is associated with insulin resistance (IR) and its phenotypic manifestations. There are clear relationships between NAFLD and obesity¹³ and between NAFLD and diabetes independent of obesity.¹⁴ Systemic IR is considered to be the key risk factor for development of NAFLD.¹⁵ The close relationship between NAFLD/NASH and type 2 diabetes mellitus (DM) leads to overlapping risk and complications and attendant economic burden for health care systems.

Despite the high prevalence of NAFLD, no safe and effective treatment is currently available.¹⁶ Management strategies for NAFLD/NASH rely primarily on non-pharmacologic measures. Since patients with NAFLD without steatohepatitis have excellent prognoses from a liver standpoint, treatments aimed at improving liver disease should be limited to those with NASH.¹

Life-style modifications are effective but adherence is difficult to maintain.¹⁷ Bariatric surgery can be performed in selective obese patients, but is too drastic to be the treatment of choice and thus it is not recommended for treating NASH.¹⁸ Vitamin E has been effective in treating nondiabetic NASH patients without cirrhosis.¹⁹ The long-term safety and efficacy of pioglitazone are not clear in NASH.^{20,21} Metformin²², ursodeoxycholic acid, omega 3 fatty acids, and statins are not considered as therapy for NAFLD/NASH patients.^{1,21}

TYPE 2 DIABETES and NAFLD/NASH

Type 2 DM involves failure of the action and utilization of insulin within the body. Type 2 sufferers have an endogenous resistance to insulin. The disease appears when they fail to manufacture sufficient insulin levels to overcome this resistance. This relative lack of insulin eventually leads to chronic hyperglycemia.

Traditionally, type 2 was known as “adult-onset diabetes” (with type 1 being referred to as “juvenile-onset” diabetes) as it generally struck adults, usually overweight, of age 45 and over. However, in recent years, the incidence of type 2 DM has skyrocketed—to the extent that it is now being termed a global “pandemic.” Type 2 DM is strongly correlated with obesity, and so this disproportionate increase is considered a reflection of the twin ills of modern life—overeating/obesity and decreased physical activity.

The 2014 CDC National Diabetes Statistics Report estimated that 29.1 million people or 9.3% of the US population have diabetes; 21 million diagnosed and 8.1 million undiagnosed.²³ Another 86 million (37% of US adults aged 20 years and older) people were estimated to suffer from pre-diabetes, a condition that increases the risk of developing type 2 DM—the more common form of the disease—as well as heart disease and stroke.

Comparable statistics may be found in both developed and developing countries around the world as the frequency of diabetes continues to rise. Global prevalence of diabetes is now estimated at more than 380 million, or about 8% of the worldwide adult population according to the International Diabetes Federation. Type 2 DM represents 85-95% of both present and future cases.²⁴

As noted above, the prevalence of NAFLD can be as high as 90–95% in obese individuals and up to 70% of patients with type 2 DM develop NAFLD.²⁵ In addition, they share similarities in their risk factors, pathogenic mechanisms and complications.

INSULIN TREATMENT

There is no known cure for diabetes. Treatment of the disease requires constant care and monitoring, along with some form of insulin or drug therapy coupled with diet and exercise.

Patients with type 2 DM have generally been prescribed a diet and exercise program as well as oral medication in order to control blood glucose levels. However, diet and oral hyperglycemic agents have failed to provide a satisfactory control of type 2 DM in a progressively larger proportion of these patients. Therefore, there is now an increasing trend to treat type 2 diabetic patients with insulin as well, in order to avoid the potential complications from hyperglycemia.

New Approaches To Insulin Therapy

In the past decade, several major studies (DCCT, UKPDS and others) have focused attention on the need for strict control of glycemia to prevent and/or reduce the risk of both the specific microvascular and the less specific macrovascular complications.^{26,27} The mounting numbers of type 2 sufferers worldwide, coupled with the growing tendency to treat this form of diabetes with insulin therapy, means that there are currently millions of individuals, adults as well as children, who must inject themselves several times each day throughout their entire lives. Injections are painful, inconvenient, and frightening for many patients. Over time reluctance to carry out injections increases and many patients become non-adherent to therapy.

In addition, the subcutaneous administration of insulin does not provide, in most cases, the fine continuous metabolic regulation that occurs normally with insulin secreted from the pancreas directly into the liver via the portal vein.

An ideal solution for treating these diabetics would be to transplant healthy insulin producing cells (pancreatic islets) into the patient. However, direct transplantation has not yet been practical. The immune system of the recipient recognizes the cells as foreign and rejects them. The side effects of drugs necessary to suppress the immune system are too severe to justify their use in otherwise healthy patients.

Consequently, research is underway to develop a new and different approach that would both improve the administration of insulin and provide a way by which the hormone can reach the liver in a physiological manner, namely, oral administration of insulin.

ORAL ADMINISTRATION OF INSULIN

Insulin injections are, intrinsically unpleasant and patients may cease to perform them, leading to a multitude of possible complications. In addition, subcutaneous injection is not the most physiologically efficient mode of insulin transfer to the body. Hence, the search for an oral form of insulin has been underway since Banting and Best's discovery of insulin in 1922. Oral insulin would free patients of the pain and inconvenience of injections while providing a more physiologically advantageous route of administration.

Proposed Mechanism

Any attempt to develop an oral insulin modality must take into account two major obstacles that result from insulin's biochemical characteristics as a polypeptide: 1) Its direct transfer across the mucosal barrier is restricted; 2) it is subject to degradation by the proteolytic enzymes located in the stomach and intestinal lumen.

To overcome these barriers, Oramed has proposed a mechanism to prevent the digestion of the introduced hormone in the gastrointestinal tract and to facilitate its physiological absorption. After performance of a range of studies for optimization of co-factors to

[figure not shown]
prevent the digestion of insulin, Oramed has identified the most efficacious formulation of encapsulated oral insulin. The proposed composition contains: (1) crystalline insulin, (2) EDTA as enhancer, (3) soybean trypsin (SBTI), and (4) omega 3-rich fish oil, in a coated capsule. These components are expanded upon in greater detail below. Each has a target function, which promotes the goals of our treatment modality. The chelating agent EDTA functions as an effective enhancer of the mixture. The SBTI prevents enzymatic degradation of the insulin by mucosal enzymes.

Modality Components

Insulin:

Structure:

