- To assess whether oral insulin may be effective in reducing liver fat content and inflammation in patients with NASH and type 2 DM.

Study Duration

Screening Phase: up to 14 days prior to placebo run-in period

Placebo run-in Phase: 2 weeks

Treatment Phase: 12 weeks

End-of-Study (EOS): After completion of 4 weeks after end of treatment

Study Population and Size

This exploratory study will first enroll 10 patients with NASH and type 2 DM.

At the completion of their 4-week follow-up period, results will be presented to the Helsinki Committee. Following approval, an additional 20 patients will be enrolled. The size of the study population was determined by the investigator (with literature review) to be sufficient to show trends of reducing liver fat content by MRI PDFF (MRI-Proton Density Fat Fraction) images, the FibroMax Test and Fibroscan including CAP.

Inclusion Criteria:

1. Male or female aged 18-70 years.
2. BMI ≥ 25
3. Known type 2 DM according to American Diabetic Association (one of the three needed): Fasting Plasma Glucose ≥ 126 mg/dl or 2h postprandial (PG) following 75g OGTT ≥ 200 mg/dl or HbA1C $> 5.7\%$ ²⁸ or on treatment with metformin
4. Abdominal ultrasound (US) proven fatty liver performed within 6 months before randomization.
5. Fat concentration in the liver of S2 (moderate steatosis, 6–32% hepatocytes with steatosis) or more as measured by Fibromax (SteatoTest and NASHTest Components, BioPredictive, Paris, France²⁹).¹ Or MRI PDFF $> 10\%$.
6. Liver enzyme abnormalities: Up to 5 times ULN.
7. Evidence of \geq stage 3 fibrosis, as determined by FibroScan
8. Signature of the written informed consent.
9. Negative pregnancy test at study entry for females of child bearing potential.

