1. Patients with active (acute or chronic) liver disease other than NASH (e.g. viral hepatitis, genetic hemochromatosis, Wilson disease, alpha-1 antitrypsin deficiency, alcohol liver disease, drug induced liver disease) at the time of randomization.
2. ALT or AST > 5 times ULN
3. Abnormal synthetic liver function (serum albumin \leq 3.5gm%, INR >1.3).
4. Known alcohol and/or any other drug abuse or dependence in the last five years.
5. Weight >120 Kg
6. Known history or presence of clinically significant, cardiovascular, gastrointestinal, metabolic (other than diabetes mellitus), neurologic, pulmonary, endocrine, psychiatric, neoplastic disorder or nephrotic syndrome.
7. History or presence of any disease or condition known to interfere with the absorption, distribution, metabolism or excretion of drugs including bile salt metabolites (e.g. inflammatory bowel disease (IBD), previous intestinal (ileal or colonic) operation, chronic pancreatitis, celiac disease or previous vagotomy).
8. Weight loss of more than 5% within 6 months prior to randomization.
9. History of bariatric surgery.
10. Uncontrolled blood pressure BP \geq 150/ \geq 95.
11. Non type 2 DM (type 1, endocrinopathy, genetic syndromes etc).
12. Patients with HIV.
13. Daily alcohol intake >20 g/day for women and >30 g/day for men.
14. Treatment with anti-diabetic medications other than metformin, such as sulfonylurea, DPP-4 inhibitors, GLP-1 receptor agonists, TZDs, etc.
15. Metformin, fibrates, statins, not provided on a stable dose in the last 6 months.
16. Patients who are treated with valproic acid, Tamoxifen, methotrexate, amiodarone.
17. Chronic treatment with antibiotics (e.g. Rifaximin).
18. Homeopathic and/or Alternative treatments. Any treatment must be stopped before the screening period.
19. Uncontrolled hypothyroidism defined as Thyroid Stimulating Hormone >2X the upper limit of normal (UNLN). Thyroid dysfunction controlled for at least 6 months prior to screening is permitted.
20. Patients with renal dysfunction: eGFR < 40 ml/min.
21. Unexplained serum creatinine phosphokinase (CPK) >3X the upper limit of normal (UNL). Patients with a reason for CPK elevation may have the measurement repeated prior to randomization; a CPK retest > 3X ULN leads to exclusion.

STUDY PERIODS

The following parameters will be measured and recorded taken at each of the visits, as specified below:

Screening Phase

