⁴Self-monitoring (finger-stick) of fasting blood glucose will required 3 days weekly in the morning and recorded in patient diaries.

TREATMENT REGIMEN

The treatment regimen will consist of a soft gelatin capsule containing 8 mg insulin, and 75 mg SBTI. Patients will take 2 capsules daily in the morning with or without food.

SAFETY EVALUATIONS

See complete instructions about Safety and Adverse Events evaluation and reporting in **Appendix B**.

- Adverse events will be collected throughout the study beginning from the time the patient signs the consent form until the EOS evaluations
- Concomitant medications/therapies will be recorded throughout the duration of study, beginning from the time the patient signs the informed consent.
- Vital signs (blood pressure, heart rate) will be measured in the sitting position after at least 5 minutes of rest at all visits
- Clinical laboratory evaluations (chemistry, hematology) will be performed at screening and at weeks 0, 4, 8, 12, and 16.
- Treatment of significant hyperglycemia, will be tailored to the medical history and needs of the patient, as per recommended treatment guidelines.
- Symptomatic hypoglycemia - Hypoglycemia as noted by a feeling of hypoglycaemia with concomitant blood glucose measurements below 70.
 - All occurrences of hypoglycemia will be treated with orange juice, 3-4 glucose tablets, or a 20% glucose solution via an I.V. bolus injection over 1 to 2 minutes and the subject will be monitored until symptoms have resolved.
 - If three or more finger stick glucose values of <50 mg/dL (2.78 mmol/L) are observed in one week within 12 hours subsequent to administration of study drug without a reasonable explanation (such as increased physical activity and/or skipped meal), the patient will be discontinued from treatment with study drug. This information will be recorded in the patient's diary and the patient will be instructed to contact the study site if this occurs. The patient will continue to be seen for all remaining study visits.
 - The site will instruct patients to immediately perform a finger stick glucose measurement if any symptoms occur that may be related to hypoglycemia (e.g., weakness, dizziness, shakiness, increased sweating, palpitations, or confusion), and to avoid delay in treating these symptoms. The measurements will be recorded in the patient diary.
 - Patients will always carry glucose tablets with them and ingest 3-4 tablets if hypoglycemia necessitates it.

REFERENCES

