Phase IIb – Type 2 Diabetes Mellitus - Clinical Trial

This multi-site, placebo-controlled, randomized, double-blinded study, conducted in South Africa, focused on the responses of 29 Type II diabetes (T2DM) patients to ORMD-0801. Volunteers received a once-daily, fixed dose of oral insulin capsules (8 mg/capsule, 2 capsules = 16 mg/day) for a period of six weeks. Three of the subjects were otherwise on diet, while 27 were on diet+Metformin (≥ 2.5 g/day) diabetes management programs before the study. The primary objective of this trial was to assess the safety and tolerability of the investigational product, by monitoring adverse events, hypoglycemia and other safety parameters throughout the study. Secondary endpoints evaluated the effectiveness of ORMD-0801 in providing glycemic control, as determined by comparison of baseline fasting blood glucose (FBG), insulin, fructosamine, c-peptide, C-reactive protein (CRP) and Hb1Ac levels to those measured after the 6-week treatment period.

The 6-week ORMD-0801 treatment regimen proved safe and tolerable, with no reports of serious AEs throughout the study period. No cumulative effects of extended exposure to

ORMD-0801 were observed, and only two mild hypoglycemic events were recorded in patient diaries (Table 1).

Table 1: Adverse Events ORMD-0801 Cohort*

Event	Severity	Action	Outcome	Notes
Hypoglycaemia	Mild	Dose not changed	Recovered	Blood sugar: 12.0 mmol/L
Hypoglycaemia	Unknown	Unknown	Unknown	Hypoglycaemic on clinical symptoms
Constipation	Mild	Dose not changed	Not recovered	
Diarrhoea and skin rash	Mild	Dose not changed	Recovered	
Diarrhoea	Mild	Dose not changed	Recovered	
Increased bowel movement	Mild	Not applicable	Recovered	

* no AEs were reported in the placebo cohort

Efficacy evaluations were performed on blood samples of 21 patients on oral insulin and 8 patients on placebo. Mean decreases in insulin and CRP levels were found to be statistically significant following the 6-week, once-daily ORMD-0801 treatment period, when compared to the placebo group (Figure 6A). These findings suggest that ORMD-0801 offered temporary relief to insulin-secreting beta cells. Moreover, the percentage of subjects demonstrating clinically relevant reductions in insulin, c-peptide, FBG and Hb1Ac levels was always higher in the ORMD-0801 cohort, when compared to the placebo (Figure 6B).

[figure not shown]

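### No eligibility criterion covers hypersensitivity to a capsule component, although each study capsule holds 75 mg of a soy-derived ingredient

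*Protocol*

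**What the plan says.** **Capsule content.** Two sections of the protocol describe the product.

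- The background section (Oral Administration of Insulin, Proposed Mechanism) begins its list with "The proposed composition contains: (1) crystalline insulin, (2) EDTA as enhancer" and ends it with "3) soybean trypsin (SBTI), and (4) omega 3-rich fish oil, in a coated capsule".
- The Treatment Regimen section describes the capsule that patients take: "The treatment regimen will consist of a soft gelatin capsule containing 8 mg insulin, and 75 mg SBTI". It names neither EDTA nor fish oil.

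**Exposure.** The Treatment Regimen section states: "Patients will take 2 capsules daily in the morning with or without food". Study Duration gives "Treatment Phase: 12 weeks", preceded by a two-week placebo run-in.

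**Eligibility.** There are 13 inclusion and 21 exclusion criteria. The closest drug-related clause is exclusion 7: "History or presence of any disease or condition known to interfere with the absorption, distribution, metabolism or excretion of drugs". The closest general clause is exclusion 6, which lists clinically significant disorders by organ system.

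**Objective.** Under Study Objectives, the primary objective is the safety of oral insulin in patients with NASH and type 2 diabetes.

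**The concern.** The protocol names a soy-derived ingredient in the study capsule, but its eligibility list has nothing on allergy to that ingredient or to any other. Eligibility is fixed in the protocol, so the gap cannot be put down to a statistical analysis plan that is not shown.

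A patient whose soy allergy is already on record could meet every written criterion and be dosed daily for 12 weeks. For such a patient the hazard is foreseeable and could be avoided at screening. It also bears on what the study is for: the primary objective is safety, the design is open-label, and no concurrent control group is described. If a reaction to a component occurred, there would be no control group to compare it with.

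**Working it through.** The check is mainly one of reading, with one multiplication. The plan gives no figure of its own to reproduce.

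**Step 1. What is in the capsule?**

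| Component | Proposed Mechanism (background) | Treatment Regimen |
|---|---|---|
| Insulin | named | named, 8 mg |
| Soybean ingredient (SBTI) | named | named, 75 mg |
| EDTA | named | not named |
| Omega-3-rich fish oil | named | not named |
| Shell | coated capsule | soft gelatin capsule |

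The background text calls SBTI soybean trypsin but says that it prevents enzymatic breakdown of insulin. I therefore read it as the trypsin inhibitor. Soy is established by both sections, and gelatin by the regimen section. Fish oil and EDTA rest on the background section alone, which calls its list a proposed composition. The protocol does not give the composition of the placebo capsule.

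**Step 2. Does any criterion cover hypersensitivity?**

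- Inclusion criteria: 0 of 13. Inclusion 12 mentions fish oil, but only among earlier treatments that must have been stopped.
- Exclusion criteria: 0 of 21. Exclusion 6 lists cardiovascular, gastrointestinal, metabolic, neurologic, pulmonary, endocrine, psychiatric and neoplastic disorders and nephrotic syndrome, but no allergic or immunologic disease. Exclusion 7 concerns what happens to a drug in the body, which is a different matter from allergy to it.
- No exclusion is left to the investigator's judgement.

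**Step 3. Is it covered elsewhere?** Medical history and medication history are taken at Visit 1, so an allergy may be recorded there, but no criterion acts on the record. Safety Evaluations deals with glucose events and monitoring. In Appendix B, the section on potential adverse events covers hypoglycemia with its symptoms, and unknowns about reproduction and fertility. It does not mention hypersensitivity.

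**Step 4. Exposure under the stated regimen.**

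- Per day: 2 capsules × 75 mg = 150 mg SBTI.
- Days: 12 weeks × 7 = 84.
- Capsules: 2 × 84 = 168.
- Total: 168 × 75 mg = 12,600 mg = 12.6 g SBTI per patient.

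Fish oil exposure cannot be worked out, because no amount is stated. The SBTI total describes scale only. The documents do not link amount to allergy risk.

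**The case against.** **The strongest case for leaving the text alone.** This is an omission. The protocol makes no false statement about allergy and does not contradict itself on it. Medical history is taken at Visit 1, and meeting the criteria does not oblige an investigator to enrol anyone. The consent pages were removed from the public copy and no investigator's brochure is shown, so either may carry an allergy warning.

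These points lower the practical risk, and they rule out saying that a site would enrol an allergic patient. They do not supply a written exclusion. A warning in another document would leave the eligibility list as it stands.

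**Stronger readings that a reader might infer, and why they fail.**

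- *The dispensed capsule contains fish oil.* It may, but only the background composition says so. The regimen section does not confirm it.
- *Earlier data already show an allergic signal.* The phase IIb adverse event table in Appendix A lists "Diarrhoea and skin rash" in the active cohort. It is a single entry, mild, with dose unchanged and the patient recovered, and no allergic cause is given. No adverse event of any kind was reported on placebo, and that group was small. As an illustration, take the numbers evaluated for efficacy (21 active, 8 placebo) as denominators and a true rate of 1/21 in both arms. The chance of no case among 8 is then (20/21)^8 = 0.68. The absence on placebo says almost nothing.
- *The chance of enrolling an allergic patient can be stated.* That needs the prevalence of soy allergy in this population, which the documents do not give. Even with an assumed prevalence, the result would not be the chance of a reaction.
- *A reaction would count as drug-related and sway the decision after the first 10 patients.* Appendix B makes relatedness an investigator's judgement on a five-level scale. Study Population and Size says that results go to the Helsinki Committee for approval and sets no threshold.

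**Conclusion.** The point holds in a limited form. Under the written criteria, a patient with a known soy allergy is eligible to take 150 mg of a soy-derived ingredient daily for 12 weeks, in a study whose primary objective is safety. None of the 34 criteria (13 + 21) addresses hypersensitivity, and nothing else in the protocol fills the gap.

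This rests on the criteria being applied as written and on the regimen section describing the capsule that is dispensed. It does not depend on fish oil, on the earlier rash or on any prevalence figure. No size of harm can be put on it from the documents. The case for change is that the hazard is foreseeable for the patients concerned and that removing it costs very little.

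**What to change.** Add one exclusion criterion: known or suspected hypersensitivity to any component of the active or placebo capsule, naming insulin, soy and gelatin. Check it from the medical history already taken at Visit 1, which comes before the placebo run-in.

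Reconcile the background composition with the Treatment Regimen section, so that the protocol gives one description of the dispensed capsule, and state what the placebo contains. Name fish oil and EDTA in the new criterion once that is settled.

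The cost is one line of protocol text, one more history question and perhaps a rare extra screen failure. The planned numbers (10 patients, then 20 more) need not change.
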